### Medical Conditions

13. History of human immunodeficiency virus (HIV) infection or positive HIV serology at screening.
14. Have a current infection or chronic infection with hepatitis B virus (HBV) at screening, that is, positive for hepatitis B surface antigen (HBsAg) and/or polymerase chain reaction positive for HBV DNA (Section 8.2.3).
15. Have a current infection with hepatitis C virus (HCV) at screening, that is, positive for HCV RNA (Section 8.2.4).
16. Have an uncontrolled chronic disease that might require multiple intermittent uses of oral corticosteroids at screening (as defined by the investigator).
17. Have uncontrolled asthma that
  - a. might require bursts of oral or systemic corticosteroids, or
  - b. required the following due to  $\geq 1$  exacerbations within 12 months before baseline
    - i. systemic (oral and/or parenteral) corticosteroid treatment, or
    - ii. hospitalization for  $>24$  hours.
18. Have known liver cirrhosis and/or chronic hepatitis of any etiology.
19. History of malignancy, including mycosis fungoides or cutaneous T-cell lymphoma, within 5 years before the screening, except completely treated in situ carcinoma of the cervix of completely treated and resolved non-metastatic squamous or basal cell carcinoma of the skin with no evidence of recurrence in the past 12 weeks.
20. Are diagnosed with active endoparasitic infections or at high risk of these infections.
21. Have a known or suspected history of immunosuppression, including history of invasive opportunistic infections (e.g., tuberculosis, histoplasmosis, listeriosis,

- coccidioidomycosis, pneumocystosis, and aspergillosis) despite infection resolution; or unusually frequent, recurrent, or prolonged infections, per the investigator's judgment.
22. Have presence of skin comorbidities that may interfere with study assessments.
  23. Have a severe concomitant illness(es) that in the investigator's judgment would adversely affect the participant's participation in the study.
  24. Have any other medical or psychological condition that in the opinion of the investigator may suggest a new and/or insufficiently understood disease, may present an unreasonable risk to the study participant because of his/her participation in this clinical trial, may make participant's participation unreliable, or may interfere with study assessments.

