### 7.1. Discontinuation of Study Intervention

When necessary, a participant may be permanently discontinued from study intervention. If so, the participant will remain in the study to complete procedures for an early discontinuation visit and post-treatment follow-up, if applicable, as shown in the SoA.

A participant should be permanently discontinued from study intervention if

- the participant becomes pregnant during the study
- in the opinion of the investigator, the participant should permanently discontinue the study intervention for safety reasons
- the participant develops a malignancy, except for successfully treated basal or squamous cell skin carcinoma
- the participant tests positive for HBV DNA (see Section 8.2.3)
- the participant tests positive for HCV RNA (Section 8.2.4)
- if the participant experiences a hepatic event or liver test abnormality as specified in the liver chemistry stopping criteria (see Section 7.1.1)
- the participant develops HIV infection
- the participant develops any infection that is opportunistic, such as active tuberculosis and other infections whose nature or course may suggest an immuno-compromised status
- the participant requires rescue medication treatment for symptoms of AD in the treatment period, and
- the participant has an AE or an SAE or a clinically significant change in a laboratory value that, in the opinion of the investigator, merits discontinuation of study intervention and appropriate measures being taken.

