### 7.1.1. Liver Chemistry Stopping Criteria

The study drug should be interrupted and close hepatic monitoring initiated (see Section 8.2.2) if 1 or more of these conditions occur:

Elevation a	Exception a
ALT or AST >8x ULN	
ALT or AST >5x ULN for more than 2 weeks	
ALT or AST >3x ULN and either TBL >2x ULN or INR >1.5	For participants with Gilbert's syndrome: If baseline direct bilirubin is >0.5 mg/dL, then doubling of direct bilirubin should be used for drug interruption decisions rather than TBL >2x ULN.
ALT or AST >3x ULN with the appearance of fatigue, nausea, vomiting, right upper quadrant pain or tenderness, fever, and/or rash	
ALP >3x ULN, when the source of increased ALP is the liver	
ALP >2.5x ULN and TBL >2x ULN	For participants with Gilbert's syndrome: If baseline direct bilirubin is >0.5 mg/dL, then doubling of direct bilirubin should be used for drug interruption decisions rather than TBL >2x ULN.
ALP >2.5x ULN with the appearance of fatigue, nausea, vomiting, right upper quadrant pain or tenderness, fever, and/or rash	
Source: FDA Guidance for Industry: Drug-Induced Liver Injury: Premarketing Clinical Evaluation, July 2009 and other consensus guidelines, with minor modifications	

Abbreviations: ALP = alkaline phosphatase; ALT = alanine aminotransferase; AST = aspartate aminotransferase; INR = international normalized ratio; TBL = total bilirubin; ULN = upper limit of normal.

a All ULN values should be age adjusted (AAULN) for participants <18 years of age.

Resumption of the study intervention can be considered only in consultation with the Lilly-designated medical monitor and only if liver test results return to baseline and if a self-limiting non-drug etiology is identified. Otherwise, study intervention should be discontinued.

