### 7.1.2. Temporary Discontinuation of Study Intervention

Temporary withholding of study intervention is required if the participant meets any of the following infection-related criteria during the study:

- Serious or opportunistic infections, as defined in Section 5.2. Study intervention is to be withheld until resolution of all acute clinical signs and symptoms, and completion of all appropriate anti-infective treatment.
- HBV DNA results that are reported as positive, or as detecting HBV DNA, but HBV DNA is below the level of quantification. In this situation, the sponsor's designated medical monitor should be contacted regarding the participant's status. HBV DNA testing is to be repeated as soon as is feasible. If HBV DNA is confirmed as positive, the participant must be permanently discontinued from study intervention as described in Section 7.1.
- If a participant <18 years of age loses a clinically significant amount of weight (below 40 kg), the investigator should assess rationale for weight loss and use clinical judgment to determine if the participant should temporarily discontinue the treatment.

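### Protocol 7.1 and 7.1.2 give different end states for an opportunistic infection, and no sentence says which governs

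*Protocol*

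**What the plan says.** Section 7.1 lists events for which a participant should be permanently taken off study intervention. One is that "the participant develops any infection that is opportunistic, such as active tuberculosis and other infections whose nature or course may suggest an immuno-compromised status".

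Section 7.1.2 lists infection-related events for which temporary withholding is required. Its first bullet covers "Serious or opportunistic infections, as defined in Section 5.2" and continues: "Study intervention is to be withheld until resolution of all acute clinical signs and symptoms, and completion of all appropriate anti-infective treatment". The bullet does not mention Section 7.1.

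The reference to Section 5.2 leads to exclusion 25b, which takes its definition of opportunistic from a published consensus paper and from Appendix 9. That appendix lists tuberculosis, and herpes zoster in any form, among infections that may be considered opportunistic. It says the list is an aid and not exhaustive. A note under exclusion 25b treats zoster as active only until the vesicles have dried and crusted.

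Two other hold rules do state how a hold becomes a permanent stop. The HBV DNA bullet of 7.1.2 says: "If HBV DNA is confirmed as positive, the participant must be permanently discontinued from study intervention as described in Section 7.1". The liver rule in 7.1.1 says: "Resumption of the study intervention can be considered only in consultation with the Lilly-designated medical monitor and only if liver test results return to baseline", adds that a self-limiting non-drug cause must be identified, and ends: "Otherwise, study intervention should be discontinued".

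**The concern.** This is a safety stopping rule whose two parts end differently for at least one named event. Under 7.1 a participant with active tuberculosis should receive no more drug. Under the first bullet of 7.1.2 the same participant is held until the infection has resolved and treatment is complete. An end point of that kind ordinarily implies that dosing may then restart. Two sites could act differently on the same case and each cite the protocol.

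What is at stake is consistent safety conduct. The choice also decides whether a participant remains on treatment to Week 16, and so belongs to the primary estimand population, but the numerical effect of that is very small.

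**Working it through.** **Setting the rules side by side**

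| Event | 7.1 | 7.1.2, first bullet | Clear overlap? |
|---|---|---|---|
| Active tuberculosis | Named example; permanent stop | Covered through 25b and Appendix 9; hold until resolution | Yes |
| Localised herpes zoster | Not named; 7.1 does not cite Appendix 9 | Covered through 25b and Appendix 9 (any form); hold | Open |
| Serious, not opportunistic | Not covered by this criterion | Hold until resolution | No conflict |

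Three ways of reconciling the text:

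1. *Hold first, then stop.* Possible, and it satisfies both rules, but it is not written for infections.
2. *7.1 reaches only infections that suggest immune compromise.* The criterion covers any opportunistic infection, and tuberculosis and infections of that kind follow as examples. They do not limit it.
3. *The verbs set the order.* 7.1 uses *should*, while 7.1.2 makes the hold a requirement. The stronger verb goes with the milder outcome, so this sets no precedence.

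Sections 8.3.3 and 8.3.3.1 and the SAP do not rank the two rules. The SAP only summarises opportunistic infections.

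**Doses at stake for one participant**

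Dosing weeks (Protocol 1.3 and 6.1) are 0, 2, 4, 6, 8, 10, 12, 14 and 16, then 20 for Q4W, or 18, 20 and 22 for Q2W, at 250 mg each from Week 4. Section 7.1 gives 0 further doses. For 7.1.2 read alone, the resume week is assumed:

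- Resume Week 8: 5 + 1 = 6 or 5 + 3 = 8 doses (1500 or 2000 mg).
- Resume Week 12: 3 + 1 = 4 or 3 + 3 = 6 doses (1000 or 1500 mg).
- Resume Week 20: 1 or 2 doses (250 or 500 mg).

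The counts stop at Week 24. Continued Access could add to them, but that addendum is not among the documents.

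**Expected frequency**

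Section 2.3 reports no opportunistic infections in its account of the three Phase 3 trials but does not give the number treated in them. I take N from 500 to 2051. The upper figure is the approximate total treated in the Phase 2 and Phase 3 AD programs, so it overstates the Phase 3 exposure. I also assume similar risk per participant. With zero events the one-sided 95% upper bound is 1 − 0.05^(1/N):

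- N = 500: 0.597%, and × 95 = 0.57 cases.
- N = 1000: 0.299%, and × 95 = 0.28 cases.
- N = 2051: 0.146%, and × 95 = 0.14 cases.

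The documents do not say whether zoster was counted as opportunistic there, so the bound does not cover it.

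**Effect on the Week 16 rate**

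The 90% Wilson interval for 40/80 is 40.96% to 59.04%, which reproduces the plan's table. At 48/95 (50.53%, near the planned 50%) it is 42.2% to 58.8%, a half-width of 8.3 points. Removing one participant gives 47/94 = 50.00% (−0.53) or 48/94 = 51.06% (+0.54).

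**The case against.** The strongest defence is that Section 5.2 already works in two tiers. Exclusion 21 bars people who "Have a known or suspected history of immunosuppression, including history of invasive opportunistic infections", with examples that end "pneumocystosis, and aspergillosis) despite infection resolution". Exclusion 25b bars opportunistic infection only within 3 months of screening or during screening, and its zoster note is a resolution rule. On this view 7.1 matches the first tier and 7.1.2 the second. That may be what was intended. The protocol does not say so, the wording of 7.1 is not limited to invasive disease, and both exclusions govern entry and not continuation.

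It can also be said that 7.1.2 sits under 7.1, so a site should read the parent list first, and that checks exist:

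- 7.1 has two stops left to the investigator's judgment.
- Section 8 sends immediate safety concerns to the sponsor to decide on continuing or stopping.
- 8.3.3 asks for sponsor discussion before a stop for an AESI, and AESIs include zoster and intracellular-pathogen infections.
- 8.3.3.1 has the sponsor identify opportunistic infections.
- 2.3 provides periodic sponsor safety reviews.

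All of this stands and makes unsupervised re-dosing unlikely. None of it sets precedence or states when dosing may resume after an infection hold.

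A reader might infer more than the documents support:

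- *That the protocol permits re-dosing after tuberculosis.* 7.1.2 gives no express permission. Resumption is implied only if the bullet is read alone.
- *That every opportunistic infection is in conflict.* For localised zoster the reach of 7.1 is undecided.
- *That exclusion 21 forbids resumption.* It is an entry criterion, and 25b points the other way for time-limited infections.
- *That the infection bullet is the only hold without a stated route to a permanent stop.* The adolescent weight-loss bullet in 7.1.2 has none either.

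**Conclusion.** The inconsistency is real and narrow. For an infection such as tuberculosis the two sections lead to different end states, and the link that the HBV DNA bullet supplies is missing. For localised zoster the documents leave the answer open. Confidence is high that no sentence sets precedence. How often it would matter is much less certain.

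Fewer than one case is expected among 95 participants at the upper bound, on the assumed Phase 3 exposure and equal risk, with zoster left unquantified. The dose counts describe a hypothetical participant at assumed resume weeks. A shift of about 0.5 points against a half-width of 8.3 is negligible for the Week 16 estimate, and both Week 16 supportive estimands keep the participant in the ITT population. This is a low-priority clarification of a safety rule and does not threaten the trial's result.

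**What to change.** Make one edit to the first bullet of 7.1.2, along these lines:

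*Hold study intervention while the infection is assessed. If it meets the opportunistic-infection criterion in Section 7.1, the participant must be permanently discontinued as described there. Resumption after resolution applies only to serious infections that do not meet that criterion, and to any opportunistic infection that the sponsor names as an exception.*

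In the same edit the sponsor states whether localised, uncomplicated herpes zoster is an exception. That is a clinical decision. Any named exception is repeated in 7.1 so that the two lists agree.

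The cost is a small protocol amendment. It needs IRB/IEC approval under Section 10.1.1, and health-authority approval if classed as substantial, so it is best bundled with the next amendment. It adds no visits, procedures or analyses. The downside is that a participant whose resolved infection meets 7.1 and is not a named exception could not resume treatment.

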#### Hepatitis

- prior to discontinuation of any immunomodulatory and/or immunosuppressive therapy due to hepatitis, including study intervention, the participant is to be referred to, evaluated, and managed by a specialist physician with expertise in evaluation and management of viral hepatitis.
- the timing of discontinuation from study intervention relative to the initiation of any antiviral treatment for hepatitis is to be based on the recommendation of the consulting specialist physician, in conjunction with the investigator, and aligned with medical guidelines and standard of care.

#### Hypersensitivity

- if the investigator determines that a systemic hypersensitivity reaction has occurred related to study intervention administration, the participant may be permanently discontinued from the study intervention, and the sponsor's designated medical

monitor should be notified. If the investigator is uncertain about whether a systemic hypersensitivity reaction has occurred and whether discontinuation of study intervention is warranted, the investigator may consult the sponsor.

### 7.1.1. Liver Chemistry Stopping Criteria

The study drug should be interrupted and close hepatic monitoring initiated (see Section 8.2.2) if 1 or more of these conditions occur:

Elevation a	Exception a
ALT or AST >8x ULN	
ALT or AST >5x ULN for more than 2 weeks	
ALT or AST >3x ULN and either TBL >2x ULN or INR >1.5	For participants with Gilbert's syndrome: If baseline direct bilirubin is >0.5 mg/dL, then doubling of direct bilirubin should be used for drug interruption decisions rather than TBL >2x ULN.
ALT or AST >3x ULN with the appearance of fatigue, nausea, vomiting, right upper quadrant pain or tenderness, fever, and/or rash	
ALP >3x ULN, when the source of increased ALP is the liver	
ALP >2.5x ULN and TBL >2x ULN	For participants with Gilbert's syndrome: If baseline direct bilirubin is >0.5 mg/dL, then doubling of direct bilirubin should be used for drug interruption decisions rather than TBL >2x ULN.
ALP >2.5x ULN with the appearance of fatigue, nausea, vomiting, right upper quadrant pain or tenderness, fever, and/or rash	
Source: FDA Guidance for Industry: Drug-Induced Liver Injury: Premarketing Clinical Evaluation, July 2009 and other consensus guidelines, with minor modifications	

Abbreviations: ALP = alkaline phosphatase; ALT = alanine aminotransferase; AST = aspartate aminotransferase; INR = international normalized ratio; TBL = total bilirubin; ULN = upper limit of normal.

a All ULN values should be age adjusted (AAULN) for participants <18 years of age.

Resumption of the study intervention can be considered only in consultation with the Lilly-designated medical monitor and only if liver test results return to baseline and if a self-limiting non-drug etiology is identified. Otherwise, study intervention should be discontinued.

### 7.1.2. Temporary Discontinuation of Study Intervention

Temporary withholding of study intervention is required if the participant meets any of the following infection-related criteria during the study:

- Serious or opportunistic infections, as defined in Section 5.2. Study intervention is to be withheld until resolution of all acute clinical signs and symptoms, and completion of all appropriate anti-infective treatment.
- HBV DNA results that are reported as positive, or as detecting HBV DNA, but HBV DNA is below the level of quantification. In this situation, the sponsor's designated medical monitor should be contacted regarding the participant's status. HBV DNA testing is to be repeated as soon as is feasible. If HBV DNA is confirmed as positive, the participant must be permanently discontinued from study intervention as described in Section 7.1.
- If a participant <18 years of age loses a clinically significant amount of weight (below 40 kg), the investigator should assess rationale for weight loss and use clinical judgment to determine if the participant should temporarily discontinue the treatment.

## 7.2. Participant Discontinuation/Withdrawal from the Study

Discontinuation is expected to be uncommon.

A participant may withdraw from the study:

- at any time at the participant's own request
- at the request of the participant's designee (for example, parents or legal guardian)
- at the discretion of the investigator for safety, behavioral, compliance, or administrative reasons
- if enrolled in any other clinical study involving an investigational product, or enrolled in any other type of medical research judged not to be scientifically or medically compatible with this study, and
- if the participant, for any reason, requires treatment with a therapeutic agent that is prohibited by the protocol and has been demonstrated to be effective for treatment of the study indication. In this case, discontinuation from the study occurs prior to introduction of the new agent.

At the time of discontinuing from the study, the participant will complete procedures for an early discontinuation visit and post-treatment follow-up, if applicable, as shown in the SoA. If the participant has not already discontinued the study intervention, the participant will be permanently discontinued from the study intervention at the time of the decision to discontinue the study.

If the participant withdraws consent for disclosure of future information, the sponsor may retain and continue to use any data collected before such a withdrawal of consent. If a participant

withdraws from the study, the participant may request destruction of any samples taken and not tested, and the investigator must document this in the site study records.

### **7.3. Lost to Follow up**

A participant will be considered lost to follow-up if he or she repeatedly fails to return for scheduled visits and is unable to be contacted by the study site. Site personnel or designee are expected to make diligent attempts to contact participants who fail to return for a scheduled visit or were otherwise unable to be followed up by the site.

## 8. Study Assessments and Procedures

- Study procedures and their timing are summarized in the SoA.
- Immediate safety concerns should be discussed with the sponsor immediately upon occurrence or awareness to determine if the participant should continue or discontinue study intervention.
- Adherence to the study design requirements, including those specified in the SoA, is essential and required for study conduct.
- All screening evaluations must be completed and reviewed to confirm that potential participants meet all eligibility criteria. The investigator will maintain a screening log to record details of all participants screened and to confirm eligibility or record reasons for screening failure, as applicable.

### 8.1. Efficacy Assessments

#### 8.1.1. Eczema Area and Severity Index

The EASI is an investigator-reported, 20-item scale that evaluates 2 dimensions of AD: extent of disease at 4 body regions (head or neck, trunk, upper and lower extremities) and 4 clinical signs (erythema, induration or papulation, excoriation, and lichenification). The clinical signs are assessed for severity on a scale of 0 (absent) to 3 (severe).

The scores are added up for each of the 4 body regions. The assigned percentages of BSA for each section of the body are 10% for head or neck, 20% for upper extremities, 30% for trunk, and 40% for lower extremities, respectively. Each subtotal score is multiplied by the BSA represented by that region.

In addition, an area score of 0 to 6 is assigned for each body region, depending on the percentage of AD-affected skin in that area: 0 (none), 1 (1% to 9%), 2 (10% to 29%), 3 (30% to 49%), 4 (50% to 69%), 5 (70% to 89%), or 6 (90% to 100%). Each of the body area scores is multiplied by the area affected. The resulting EASI ranges from 0 to 72 points, with the highest score indicating worse severity of AD (Hanifin et al. 2001). The recall period of this scale is present time.

Assessors must be trained and certified by the sponsor prior to conducting this assessment. A single assessor should be assigned to each participant for as many visits as possible to avoid inter-assessor variability in scoring. The recall period of this assessment is present time.

